4. STUDY POPULATION

4.1 Population (base)

Dutch speaking older adults between 60 and 80 years old (male and female) from the general population in the Netherlands will be selected as participants for this study. Individuals who are interested in participating in the study based on the advertisements, will be screened by phone. During the first phone call questions will be asked about (i) personal data, (ii) presence of sleep problems, and (iii) availability during the study period via a screenings questionnaire. If the person seems eligible based on their answers to these questions, a PIF and IC will be sent to them by mail. A second phone call will be scheduled at least one week after the first phone call to address any questions related to the PIF. After receipt of verbal consent, during the second phone call, a screening at the study center will be planned. During the screening visit, which will take approximately 30 minutes, participants can give written informed consent. Thereafter, two non-fasted blood samples will be drawn (3.5 ml + 2 ml =5.5 ml), and two questionnaires will be filled out: (i) Insomnia Severity Index (ISI, to assess insomnia symptoms) and (ii) Munich chronotype Questionnaire (MCTQ, to assess chronotype). The latter will not be used as a screeningstool but is collected as a baseline characteristic. We will include participants scoring ≥ 10 on the ISI. Additionally, we believe that the possible outcomes of this study will be relevant for older adults with sleep problems since both ageing as well as sleep problems are closely linked to the circadian clock. Potential participants will be recruited through advertisements in newspapers and local radio. For practical reasons and since the 'Vitality Clubs' are located here, participants will be sought in Leiden and surroundings.

4.2 Inclusion criteria

In order to be eligible to participate in this study, all participants must meet all of the following criteria:

- Aged between 60 and 80 years old
- Retired
- Long lasting sleep problems (as assessed by a the screening questionnaire administered telephonically and by the ISI which will be filled out during the screening visit)
- Access to and ability to use a smart phone (Android or Apple)

4.3 Exclusion criteria

A potential subject who meets any of the following criteria will be excluded from participation in this study:

- Currently employed or working
- Participation in any sort of fasting regimen (e.g. intermittent fasting or Ramadan)
- Experienced recent (<6 months) adverse life events (e.g., death of partner)
- Abnormal values in glucose metabolism, thyroid, liver or kidney function, or inflammation markers that after examination of the study doctor need immediate attention of a general practitioner or specialist.
- Diagnosed clinical depression
- Diagnosed neurodegenerative diseases (e.g. dementia or Parkinson's disease)
- Diagnosed sleep apnoea
- Diagnosed restless legs syndrome
- Use of beta-adrenergic blocking agents
- Use of sleep medication*
- Injuries or other severe physical conditions (such as active arthrosis) that inhibits physical activity
- Travelled across time zones one week prior to start of study

*If participants are willing to cease usage of sleep medication 2 weeks before baseline measurement until the end of the study, they can be included. An exception must be made for individuals with amitriptyline prescribes as sleep medication due to its side effects of discontinuing use.

For this study we want to use CTcue to facilitate the inclusion of patients.

4.4 Sample size calculation

The sample size was calculated for the primary outcome of mean change of insomnia symptoms severity from baseline and after completing the active morning vs. active evening measured by the ISI which is proven to be a well validated and sensitive questionnaire for mapping insomnia severity. All sample size calculations were based on statistical power of 0.80 and a 2-sided α of 0.05. The calculations were performed using GPower v.3.1 (Kiel University, Germany). To the best of our knowledge, there is no literature available on the effect size of physical activity timing on insomnia severity. Therefore, estimations were based on treatment effect size of guideline recommended physical activity on insomnia severity (measured by ISI) found in a previous randomized controlled trial(32). Assuming a standard deviation (SD) of 5.4, a total of 36 participants are required to detect a minimal difference of 2.6 points on the ISI. Considering a possible dropout rate of 10% during the study, the target sample size is 40 participants.

5. TREATMENT OF SUBJECTS

5.1 Investigational treatment

5.1.1 Active morning and active evening intervention

Participants will participate in three interventions consisting each of a 14-day physical activity regimen. The active morning and active evening intervention are equal in content but in the active morning group, participants will be instructed to be active between 10:00 and 11:00 hour in the morning and the active evening will be instructed to be active between 19:30 and 20:30 in the evening. Both groups will be instructed to refrain from any moderate to vigorous exercise for the rest of the day. Per intervention, a total of eight Vitality Club training session will be organised given by a trained sports coach or physical therapist specialized in geriatric physical therapy. These training sessions will be different in character (e.g., a game of volleyball and a circuit training) but will all contain a combination of strength and endurance training tailored for older adults. Literature is inconclusive whether it is more beneficial to participate in aerobic endurance training (AET) or resistance exercise training (RET). AET is more beneficial for body composition and endurance and RET is more beneficial for muscle mass and strength. Both types of exercises contribute to important components of QOL and healthy ageing and therefore we believe that it is most valuable/effective to compose a training regimen containing both AET and RET exercises.(34) During the weekends (Saturday and Sunday), there will not be a Vitality Club sessions. Instead, participants will be asked to perform a 'relative rest' session. On a 'relative rest' day, participants will be given the opportunity to recover from the vitality club. Yet, since we do not want to lose the effect of the intervention, we ask the participants to perform any light activity during the given window of time of the intervention arm. For one weekend day (Saturday) in the measurement week, or when participants are unable to participate in the Vitality Club, they will be asked to perform some sort of physical activity/exercise at home (the 'Active@Home' program) between the above-mentioned times (depending on the intervention). Participants will be handed multiple training schedules/options for the Active@Home option corresponding to a metabolic equivalent of 3-8 MET's (moderate to vigorous physical activity) for one hour. Participants will also be asked to refrain from activities with equal MET's for the rest of the day to ensure that their physical activity peak will only be in the morning or evening (depending on the intervention). To ensure participants will stay well informed, they will be handed a booklet with all necessary information and a day by day description of all measurements and exercise program ('E4. Studieboekje').

5.1.1 Sedentary period

Literature shows that physical activity improves insomnia severity.(32) In previous studies, the follow-up period was at least 3 months. As we will use a shorter follow-up period in this study, we have included a sedentary period, to assess the effect of physical activity versus no physical activity. This intervention additionally examines the effect of physical activity timing. In order to verify that the exercise intervention provided in this study has a similar positive effect, we will compare our interventions to this sedentary period. All participants will start with a 14-day sedentary period. They will be instructed to refrain from any moderate to vigorous exercise. Compliance to these instructions will be observed through the wrist worn accelerometer. Where necessary, participants will be reminded of the instructions.

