3. STUDY DESIGN

We will perform a randomized two-armed cross-over study. Both groups will start with the sedentary period. Randomization will be performed at the moment of enrollment using a computer-based statistical program (depending on the intervention arm, participants will then undergo the active morning intervention or active evening intervention first, followed by the remaining intervention. There will be a total of two washout periods both lasting 7 days, one between the sedentary period and first intervention and one between the first and second intervention to prevent or minimize 'carry over' of previous intervention effect. The two interventions and the sedentary period will last 14 days each and contain a 'calibration period' (7 days) and a 'measurement week' (7 days). The former will serve as an adjustment period in which we hypothesize that our endpoints of interest will adjust to the new exercise regimen. After the calibration period, the measurement week starts in which all endpoints will be measured. Apart from the measurements, there are no differences in intervention between calibration and measurement week. The total study duration will be 8 weeks and the study will largely take place at the participants' home except for the training sessions (Vitality Clubs) that will take place at an outdoor sports facility in the municipality of Leiden and the study site visits which will take place in the LUMC. **Figure 3.1** shows a schematic overview of the study outline and **Appendix A** shows an example of the study schedule during the active morning intervention.

[figure not shown]

Figure 3.1. Schematic overview of the study

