3.1 Design justification

A cross-over study allows the response of a participant to morning exercise to be contrasted with the same participant's response to evening physical activity and sedentary period. Removing inter-participant variation allows for more efficient and precise estimation than similar sized studies with parallel intervention groups.

As we study the effect of timing on change in insomnia severity and changes in the rhythm of multiple processes hypothesized to be altered rapidly through environmental cues, such as daylight changes over the season, a randomized cross-over study which is usually bound to short-term outcomes is the most suitable design for this study.

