8.2 Randomisation, blinding and treatment allocation

As this is a cross-over study, participants will undergo all three conditions. Participants will be randomised into two groups at enrolment using a computer-based statistical program. Both groups will start with sedentary period where after the first group will start with the active morning first followed by the active evening. For the second group, the order of the two activity interventions will be reversed (sedentary period- active evening- active morning). Blinding will not be possible in this study. However, we will minimise the interference of the researchers that will perform the analyses during the study by hiring a research nurse to lead the study. If necessary, the research nurse will be assisted by medical students.

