10.2 Secondary study parameter(s)

Secondary endpoints include changes in:

Biological clock function

- Clockgene expression
- Core body temperature (°C)
 - Diurnal pattern
 - Time of lowest temperature
- Melatonin
 - Dim light melatonin onset (DLMO)

Physiological parameters

- Heart rate
 - Diurnal pattern
 - Average
 - Resting heart rate
 - Minimum/peak heart rate (5 and 95 percentile)
- Heart rate variability (HRV)
- Breathing rate
- Oxygen saturation (SpO2)

Mental health

- Subjective mood
 - Diurnal pattern of:
 - Positive affectivity
 - Negative affectivity
 - Energy
 - Fatigue

- Cognition
- (objective) Electrodermal activity (emotional arousal and stress)

Behavioural factors

- Food intake
 - Frequency
 - Timing
- Habitual sleep (**Table 8.1**)
 - Sleep latency (min)
 - Duration (min)
 - Efficiency (%)
 - Sleep phases (%, min)
 - Awakenings at night (x, min)
 - Rested feeling (subjective, 0-7)
 - General satisfaction with sleep (subjective, 0-7)

Biochemistry

- Glucose metabolism
- Inflammatory markers
- Liver function
- Kidney function
- Thyroid function
- Bone metabolism markers
- White blood cell count

Changes between active morning and active evening will be assessed. Diurnal patterns will be calculated through the hourly mean level of for example glucose and will be displayed for each condition. Additionally, we will perform sensitivity analysis for both the primary endpoint as all secondary endpoints by analyse the changes between the sedentary period & active morning, and the sedentary period & active evening. Assuming the data is normally distributed, a paired t-test will be used for all analyses and data will be shown in as mean difference, SD, and p-value.

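### The sedentary period always comes first, so its comparisons with the active periods cannot separate exercise from time without an assumption about period effects that the plan does not make

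*Combined protocol and SAP*

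**What the plan says.** Three places in the protocol fix the position of the sedentary period. Section 3: "Both groups will start with the sedentary period". Section 5.1.1, under the heading Sedentary period: "All participants will start with a 14-day sedentary period". Section 8.2: "Both groups will start with sedentary period where after the first group will start with the active morning first", with the two active periods reversed in the second group. The sequences are therefore sedentary-morning-evening (S-M-E) and sedentary-evening-morning (S-E-M).

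The Sedentary period section gives the purpose of this period as "to assess the effect of physical activity versus no physical activity". It then states the aim of the comparison: "verify that the exercise intervention provided in this study has a similar positive effect, we will compare our interventions to this sedentary period". Section 3.1 presents the within-person contrast of morning exercise with the same participant's "response to evening physical activity and sedentary period", without distinguishing randomised from fixed order.

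Section 10.2 turns this into an analysis. The team will "perform sensitivity analysis for both the primary endpoint as all secondary endpoints by analyse the changes between the sedentary period & active morning", and likewise sedentary versus active evening. Paired t-tests are to be used throughout, reported as mean difference, SD and p-value. The plan contains no period or time term, no stated assumption about period effects and no caveat about the fixed order. The two 7-day washouts are justified by carry-over only.

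**The concern.** A paired comparison of an active period with a period that always precedes it is a before-after comparison. Anything that moves the outcome over the eight weeks is counted as an effect of exercise, or subtracted from one.

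The protocol itself gives grounds to expect movement. Section 3.1 names seasonal daylight as a cue that can quickly alter the rhythms under study. Entry requires an ISI of at least 10, on the scale later used as the outcome. Section 4.3 admits users of sleep medication who stop it two weeks before baseline. Blinding is not possible.

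At stake is the inference promised in the Sedentary period section. A significant sedentary-active difference could be reported as confirmation that the 14-day regimen works, and a null one as evidence that it does not. Neither would follow. The label in section 10.2 adds to the difficulty: these contrasts ask a different question from morning versus evening, so they do not test the robustness of the primary result.

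**Working it through.** **Inputs.** Section 4.4: SD 5.4, difference 2.6 ISI points, power 0.80, two-sided 0.05, 36 evaluable, 10% dropout, target 40. Sections 3 and 8.2: sequences S-M-E and S-E-M. Assumed, because the documents give no figure: the size and shape of any ISI drift.

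**The plan's own figure.** A paired t-test with standardised difference 2.6/5.4 = 0.481 has power 0.802 at n = 36 (non-central t), and 36/0.9 = 40. The stated sample size is reproduced when 5.4 is read as the SD of the paired difference. It applies to morning versus evening; none is stated for the sedentary contrasts.

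**What is estimable.** Take the model: outcome = participant + period (three free levels) + condition (S, M, E). For 40 participants it has 40 + 2 + 2 = 44 columns and rank 43. The redundant direction is (period 2, period 3, M, E) = (-1, -1, +1, +1): a shift common to periods 2 and 3 is indistinguishable from an exercise effect common to both active periods. Morning-evening is estimable; morning-sedentary and evening-sedentary are not. Adding the baseline as a further no-exercise period gives rank 44 of 45 and the same answer.

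**Bias of the planned contrasts.** Let P2 and P3 be the time shifts of periods 2 and 3 from period 1. With equal sequence groups, each sedentary contrast estimates its true effect plus (P2 + P3)/2. In the morning-evening contrast the shifts cancel.

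**Illustrative rejection rates.** n = 36, no exercise effect, SD of differences 5.4 borrowed from section 4.4. For a fall of d points per period:
- linear: bias (d + 2d)/2 = 1.5d, with SD √(5.4² + (0.5d)²), because the two sequences differ in timing;
- plateau after period 2: bias (d + d)/2 = d, with SD 5.4.

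| d (ISI points) | Linear: bias | Linear: rejects | Plateau: bias | Plateau: rejects |
|---|---|---|---|---|
| 0.5 | 0.75 | 13% | 0.5 | 8% |
| 1.0 | 1.5 | 36% | 1.0 | 19% |
| 1.5 | 2.25 | 67% | 1.5 | 37% |

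At d = 1.0, varying the SD from 7.0 down to 4.0 gives 24% to 58% (linear) or 13% to 31% (plateau). A mean shift of 0.6 points is enough to double the nominal 5% to 10%. In simulation, morning-evening stayed at about 5% in every drift scenario tried.

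**Would assuming linear time rescue the contrasts?** It identifies them, at a price. With independent errors, σ² = 5.4²/2 = 14.58. From the three period means, the average exercise effect is 2 × (period 2) − (period 1) − (period 3), with variance (4 + 1 + 1) × 14.58/36 = 2.43. A single sedentary contrast adds a quarter of the morning-evening variance, 0.81/4 = 0.2025. The SE is √2.6325 = 1.62, against 5.4/√36 = 0.90 without a time term. Power for 2.6 points falls from 80% to 35% (69 df). Adding the baseline ISI at day 0 as a second no-exercise point changes this only to SE 1.58 and 37%. If drift in fact stops after period 2, with period means 0, −1, −1 and no exercise effect, the formula gives 2(−1) − 0 − (−1) = −1: the full one-point drift remains as bias.

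**The case against.** The strongest reply is about weight. Section 2 does not list exercise versus no exercise as an objective. The primary test (10.1) and the sample size (4.4) concern morning versus evening. Section 10.2 ranks the sedentary contrasts as sensitivity analyses, and the fixed order is stated openly three times. All of this stands. It confines the problem to auxiliary contrasts but does not support the inference that the Sedentary period section promises from them.

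A second reply is that the illustrated drifts are hypothetical, all of them improvements, with an SD taken from another contrast. That also stands. A worsening over time would hide a benefit instead. The figures show sensitivity to drift, not an expected error rate.

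A third reply is that the study has data from before any exercise. It does, and more than a baseline alone:
- ISI, HbA1c and haematology are taken at screening, at baseline and after the sedentary period.
- Fasted chemistry is taken at baseline and after the sedentary period.
- The wearable is worn throughout, the sleep mat is installed beforehand, and Appendix B gives 42 days (3 × 14) for their measures, so both sedentary weeks are covered.

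These data can describe the course before exercise, but they do not restore identification. From baseline onward they mix time with any effect of the instruction: "They will be instructed to refrain from any moderate to vigorous exercise". Screening precedes that instruction, but screening ISI is exposed to regression to the mean from the entry threshold. A reader might infer that the instruction necessarily lowers activity. The documents do not establish that: section 8.3 speaks of participants keeping an already inactive lifestyle. Clock-gene RNA, melatonin, the momentary mood assessments and the food diary have no measurement planned before the sedentary period's own measurement week.

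**Conclusion.** The point holds for the sedentary contrasts. With unrestricted period effects they are not estimable. They become so only if period effects are assumed to be zero or of a fixed form such as a straight line, and the plan neither states nor supports such an assumption. They therefore cannot deliver the assessment or verification of an exercise effect that the Sedentary period section describes, and the paired t-tests would credit any time trend to exercise.

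Three stronger readings are not supported:
- A reader might infer that the primary result is compromised. It is not: morning versus evening is a randomised-order contrast, and with balanced sequence groups the period shifts cancel.
- A reader might infer that the contrasts can never be identified. The limit is conditional on leaving period effects free.
- A reader might take 36% or 67% as the trial's actual false-positive rate. The documents give no ISI trend, so the true bias is unknown and could be nil.

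This is a fault in a promised inference, worth correcting before analysis, and not a threat to the trial's main question.

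**What to change.** Keep the design and change the wording.

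1. In the section headed Sedentary period, replace the two statements of purpose with: *The sedentary period is always first. Comparisons of the active periods with it are supplementary, fixed-order before-after comparisons. Without an assumption about period effects they cannot separate exercise from time, and no causal or efficacy conclusion about exercise will be drawn from them.*
2. In section 10.2, call these contrasts supplementary before-after comparisons instead of a sensitivity analysis. Cross-refer by the heading Sedentary period, because the number 5.1.1 is used twice. Align the closing reporting sentence so that these contrasts are given as mean difference with 95% confidence interval and no confirmatory p-value, while the paired t-test stays for morning versus evening. Otherwise the two sections would conflict.
3. In section 3.1, state that only morning versus evening is a randomised-order contrast.
4. Optional and descriptive only: show the pre-exercise course from data already planned. Use screening, baseline and end-of-sedentary values for ISI, HbA1c and haematology; baseline and end-of-sedentary values for fasted chemistry; and sedentary week 1 against week 2 for wearable and sleep-mat endpoints. Note that these mix time with any effect of the instruction to avoid moderate-to-vigorous exercise, and that screening ISI is subject to regression to the mean.

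Cost: no new visits, samples or participants, and no change to randomisation or the primary test. The trial gives up a causal claim about exercise versus no exercise that its design cannot support.

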5.2 Use of co-intervention

Not applicable

